8.10.3. Study holding rules

The safety holding rules which will be checked by the iSRC during each safety evaluation are defined below ([Table 22](#)). Please refer to [APPENDIX C](#) for the definition of the Food and Drug Administration (FDA) Toxicology Grading Scale for laboratory abnormalities in healthy subjects.

These holding rules have been written under the assumption that the safety data will be available from all subjects. If the data from all subjects are not available (i.e. in case a subject is lost to follow-up), then the holding rules will be assessed on a pro-rata basis.

Table 22 List of holding rules

| Holding rule N° | Event | Number of subjects | |
|-----------------|--|----------------------------------|----------------------------------|
| | | Step 1 | Step 2 |
| 1a | Death or any life-threatening SAE | ≥ 1 | ≥ 1 |
| 1b | Any withdrawal from the study (by investigator or subject request) following a Grade 3 AE that cannot reasonably be attributed to a cause other than vaccination | ≥ 1 | ≥ 1 |
| 1c | Any local or general solicited AE leading to hospitalisation , or fever >40°C (104°F) that cannot reasonably be attributed to a cause other than vaccination, or necrosis at the injection site, within the 7-day (Day 0-Day 6) post-vaccination period | ≥ 1 | ≥ 1 |
| 2a | Any Grade 3 solicited local AE lasting 48h or more in an investigational group, within the 7-day (Day 0-Day 6) post-vaccination period | ≥ 5/15 and ≥ 2 subjects/group | ≥ 8/30 and ≥ 2 subjects/group |
| 2b | Any Grade 3 solicited general AE lasting 48h or more in an investigational group, that cannot reasonably be attributed to a cause other than vaccination, within the 7-day (Day 0-Day 6) post-vaccination period | ≥ 5/15 and ≥ 2 subjects/group | ≥ 8/30 and ≥ 2 subjects/group |
| 2c | Any Grade 3 unsolicited AE in an investigational group, that cannot reasonably be attributed to a cause other than vaccination, within the 7-day (Day 0-Day 6) post-vaccination period or Any Grade 3 abnormality in pre-specified haematological or biochemical laboratory parameters* in an investigational group within the 7-day (Day 0-Day 6) post-vaccination period | ≥ 5/15 and ≥ 2 subjects/group | ≥ 8/30 and ≥ 2 subjects/group |

* i.e. haemoglobin, WBC, platelets, creatinine, ALT and AST

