- For **solicited symptoms**, the analysis will exclude subjects with missing or un-evaluable measurements (e.g. total analysis of solicited symptoms will include all vaccinated subjects with documented solicited symptom sheets).
- For the **unsolicited symptoms** and concomitant medications/ products/ vaccinations, subjects who did not report unsolicited symptoms/concomitant medications/ products/ vaccinations will be treated as subjects without unsolicited symptoms or concomitant medications/ products/ vaccinations, respectively.
- Note that for all tables described in this section, the way the percentage of subjects will be derived will depend on the event analysed (see table below for details). As a result, the N value will differ from one table to another.

Event	N used for deriving % per subject
Concomitant vaccination	All subjects with study vaccine administered
Solicited general symptom	All subjects with at least one solicited general symptom documented as either present or absent (i.e. symptom screen completed)
Solicited local symptom	All subjects with at least one solicited local symptom documented as either present or absent (i.e. symptom screen completed)
Unsolicited symptom	All subjects with study vaccine administered
Concomitant medication	All subjects with study vaccine administered

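### Unsolicited adverse event rates count subjects lost within the 30-day window as event-free, and the two denominator rules for solicited symptoms do not match

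*SAP*

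**What the plan says.** **Unsolicited events.** In SAP Amendment 2, section 8 (Safety/reactogenicity), "subjects who did not report unsolicited symptoms/concomitant medications/ products/ vaccinations will be treated as subjects without unsolicited symptoms". Protocol section 10.5 carries the same rule, so it is not new in the SAP. The table in SAP section 8 that fixes N gives the denominator for an unsolicited symptom as "All subjects with study vaccine administered". Neither place requires a returned diary card, a visit or any other contact in the 30-day window.

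**Solicited events.** The same SAP section has two statements. The bullet says "the analysis will exclude subjects with missing or un-evaluable measurements", and gives as its example that the "total analysis of solicited symptoms will include all vaccinated subjects with documented solicited symptom sheets". The N table uses, for general symptoms, "All subjects with at least one solicited general symptom documented as either present or absent", with a parallel row for local symptoms. Both rows carry the gloss that the symptom screen was completed.

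**Endpoints affected.** SAP section 5.1 lists as primary endpoints the occurrence of each solicited local and general event over 7 days and of any unsolicited event over 30 days, after each dose.

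**The concern.** For unsolicited events, the rule does not separate a subject who was followed and had nothing to report from one who was not followed. The first is a true negative. The second is unknown but is scored as a negative. The resulting error has one direction: it can lower a primary safety rate and its upper limit, never raise them above what full follow-up would have given. This is the first study to give UspA2 to humans, its groups are of about 15 or 30, and withdrawals are not replaced (Protocol section 9.2). Readers will look to the upper limits for what cannot be ruled out.

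For solicited events, the endpoint is each symptom separately, so the denominator matters at the level of the single item. The bullet and the table can give different N for the same symptom, and nothing says which one prevails.

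**Working it through.** **1. The plan's own figures.** The exact (Clopper-Pearson) 95% upper limit for 0 events in n is 1 − 0.025^(1/n). For n = 15 this is 21.8%, as in Protocol Table 23; the other rows of that table also reproduce. The chance of seeing at least one event of true rate 5% in 30 subjects is 1 − 0.95^30 = 78.5%, as stated in Protocol section 10.3. Both figures presume that all 15 or 30 subjects are observed.

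**2. Effect of the unsolicited rule on the expected rate.** Let p be the true rate and m the fraction of vaccinated subjects unobserved in the window. If the unobserved have the same true rate, the expected reported rate is p(1 − m), a bias of −pm. The documents give no value for m; 5% to 20% is assumed here.

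| True rate | m = 5% | m = 10% | m = 20% |
|---|---|---|---|
| 10% | 9.5% | 9.0% | 8.0% |
| 30% | 28.5% | 27.0% | 24.0% |

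At m = 0 the bias is zero.

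**3. Effect on the reported interval.** Assume 2 of 15 (13.3%) or 3 of 30 (10%) unobserved, with all events coming from observed subjects:

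| Vaccinated / observed | Events | All vaccinated (SAP rule) | Observed only |
|---|---|---|---|
| 15 / 13 | 0 | upper limit 21.8% | upper limit 24.7% |
| 15 / 13 | 3 | 20.0% (4.3–48.1) | 23.1% (5.0–53.8) |
| 30 / 27 | 0 | upper limit 11.6% | upper limit 12.8% |
| 30 / 27 | 6 | 20.0% (7.7–38.6) | 22.2% (8.6–42.3) |

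With 20% unobserved and no events, the observed-only upper limits are 26.5% (0/12) and 14.2% (0/24). The chance of detecting a 5% event among 30 vaccinated falls from 78.5% to 1 − 0.95^27 = 75.0% with 27 observed, and to 1 − 0.95^24 = 70.8% with 24.

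**4. The solicited rules side by side.** Take a subject with headache recorded for a dose and no temperature.
- The bullet, read symptom by symptom, leaves this subject out of N for fever.
- The table keeps this subject in N for general symptoms, because one general symptom is documented. If that N serves the fever row, the subject adds 1 to the denominator and 0 to the numerator, just as an afebrile subject would.
- The bullet's example (documented sheets) and the table's gloss (completed screen) both work at the level of the sheet, so neither settles the case of a single blank item.

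**The case against.** Much can be said for the plan, and several stronger readings fail.

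- *A reader might infer that everyone who filed no report is unobserved.* The documents do not support that. Unreturned diary cards are chased (Protocol section 5.6.16), subjects are asked a non-leading question (8.3.3.1), and those who miss visits are contacted (9.2.1). Most non-reporters will be followed subjects without events, for whom the rule is right.
- *A reader might infer that drop-out for poor tolerability is hidden.* Largely it is not. Events leading to withdrawal are collected until study conclusion (8.3.1) and reported (SAP section 7.2.2), and stopping vaccination need not end follow-up (Protocol section 9.2.2). Only silent loss within a 30-day window matters. A subject who leaves after Day 30 and before Dose 2 was fully observed for Dose 1.
- *A reader might infer a contradiction with the holding rules*, which say of incomplete data "then the holding rules will be assessed on a pro-rata basis". There is none. Those rules adjust interim thresholds over Day 0 to Day 6; the SAP rule governs 30-day tables. Pro-rating bears only on rules 2a to 2c, since 1a to 1c are met by a single subject. The decisions to proceed do not use the SAP rule.
- *A reader might infer that the SAP scores a blank solicited item as absent.* No sentence says so, and the bullet points the other way. The supported finding is a mismatch.

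What stands is that none of these provisions changes the unsolicited denominator. The conditional according-to-protocol safety analysis (SAP section 7.1.2) does not do so either. It runs only if at least 10% of a group is excluded. Its criteria (6.1.2.1) concern eligibility, vaccination and the Day 90 blood sample, not diary return.

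**Conclusion.** The point holds as a low-cost improvement. If any vaccinated subject is lost within a 30-day window, the all-vaccinated rate of unsolicited events and its upper limit are either unchanged or too low relative to complete follow-up. The size depends on a missing rate that the documents do not give. At an assumed 10% unobserved, a true 10% rate would be reported on average as 9.0%, and a zero-event upper limit in a group of 30 as 11.6% instead of 12.8%. These figures assume that lost subjects have the same event rate as followed ones. A higher rate among them would enlarge the bias and a lower one would shrink it, but neither would reverse it. With complete follow-up there is no effect.

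For solicited symptoms, the bullet and the N table do not match at item level and must be reconciled. Counting an undocumented item as no event is one possible outcome of that ambiguity, not a stated rule. The analyses are descriptive, and nothing here questions the conduct of safety monitoring.

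**What to change.** In SAP section 8:

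1. **Unsolicited events.** Keep the all-vaccinated percentage. For each dose and overall, add the number of subjects without documented follow-up for the window and the percentage, with exact 95% CI, among subjects with documented follow-up. Define this as the diary card returned, or the 30-day visit or contact done. As the first card stops at Day 6, the card meant should be the second; overall, follow-up should cover every dose received. N should depend on follow-up status only. Adding unfollowed subjects because they reported an event would push the rate up. For example, take 30 vaccinated, 26 followed with 4 events, and 4 unfollowed of whom 2 reported. Followed only gives 4/26 = 15.4%, all vaccinated 6/30 = 20.0%, and the mixed denominator 6/28 = 21.4%. Events from subjects without documented follow-up stay in the all-vaccinated figure and are shown separately.
2. **Solicited events.** Reconcile the bullet and the table: for each individual symptom and dose, N is the subjects with that symptom documented as present or absent.

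The cost is SAP wording, one follow-up flag and a little extra tabulation. Visits and diary transcription are already eCRF items (Protocol Tables 5 and 6); whether a telephone contact in place of a visit is recorded should be confirmed. Some rates will look slightly less favourable.

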8.1. Data presentation description

The following decimal description will be used for the demography and safety/reactogenicity.

Display Table	Parameters	Number of decimal digits
All summaries	% of count, including LL & UL of CI	1
All summaries	% of difference, including LL & UL of CI	2
Demographic characteristics	Mean, median age	1
Demographic characteristics	SD (age)	2
Immunogenicity	GMT ratio	2

The following data presentation description will be used for the immunogenicity analyses.

Statistical Analysis Plan

Study alias & e-track number(s): NTHI MCAT-001 (201281)

Component	GMC/T	Assay		Assay cut-off	Number of decimal digits		Tick marks on RCC's		
		method	Unit		GMC/T	GMC/T ratio			
						Low value	High value		
Anti-PD	GMC	ELISA	EL.U/ml	153	1	2	1	10000	
Anti-PE	GMC	ELISA	EL.U/ml	8	1	2	1	10000	
Anti-PiA	GMC	ELISA	EL.U/ml	7	1	2	1	10000	
Anti-UspA2	GMC	ELISA	EL.U/ml	18	1	2	1	10000	

9. CONDUCT OF ANALYSES

9.1. Sequence of analyses

- The analysis of data up to Visit 6 (Day 90, end of Epoch 001) will be performed in a first step. This analysis will include:
 - The final analysis of all immunogenicity results (including CMI), solicited AEs post-Dose 1 and post-Dose 2,
 - The assessment of unsolicited AEs up to 30 days post-Dose 1 and post-Dose 2, and of SAEs and pIMDs up to 30 days post-Dose 2 on as cleaned as possible data. No individual listings will be written at this stage.

This analysis will be documented in a statistical report. At this point, the GSK statistician will be unblinded (i.e. will have access to the individual subject treatment assignments).

- The analysis of Epoch 002 (from Visit 7 [Day 210] up to Visit 8 [Day 420]) will be performed in a second step, once those data will be available and cleaned. This analysis will include:
 - The final analysis of all immunogenicity results (including CMI) up to Visit 8 (Day 420).
 - SAEs and pIMDs up to Visit 8 (Day 420) on cleaned data.

In addition, all previous analyses will be re-produced based on cleaned data at this point.

Individual listings will only be provided at this stage.

Description	Analysis ID	Disclosure Purpose
Analysis up to Visit 6 (Day 90)	E1_02	Internal
Final analysis (up to day 450)	E1_01	CTRS & Clinical Study Report

Study alias & e-track number(s): NTHI MCAT-001 (201281)

9.2. Statistical considerations for interim analyses

Not applicable.

10. CHANGES FROM PLANNED ANALYSES

None.

11. REFERENCES

The exact 95% CIs for a proportion within a group will be calculated from Proc StatXact [Clopper CJ, Pearson ES. The use of confidence or fiducial limits illustrated in the case of binomial. *Biometrika*. 1934;26:404-413].
